5.7.2.3. PK Parameter Summarization

The plasma PK parameters, C_{max} , AUC_n , AUC_{last} , AUC_{inf} , $T_{1/2}$, CL/F , Vz/F , MRT, $RA(C_{max})$, $RA(AUC_n)$, $RA(AUC_{last})$, $MR(C_{max})$, $MR(AUC_n)$, $MR(AUC_{last})$, $MR(AUC_{inf})$ and others as applicable will be listed by patient and summarized by dose level and treatment period, including number of observations (n), arithmetic mean, SD, CV%, minimum, median, maximum, geometric mean, geometric CV%. T_{max} will be listed by patient and summarized by dose level, and treatment period, including number of observations (n), minimum, median, and maximum.

The arithmetic mean, median, minimum, maximum, and geometric mean will be presented to the same decimal places as the individual values. SD will be presented to the same decimal place as

the mean. CV% and geometric CV% will be presented to 1 decimal place. PK parameters of secondary interest (R-square, R-square adjusted, the number of data points used for estimating λ_z , the upper and lower time point used for estimation of λ_z , λ_z itself, and $AUC_{\text{extrap}}\%$ will be listed by patient to enable verification of the exclusions, if any, of data from the summary statistics of the PK parameters of primary interest.

If a patient is treated with dose-modification or dose-interruption, concentrations from this patient on next PK collection date onward may be flagged and excluded from the summary statistics if deemed as appropriate.

5.7.2.4. Dose-proportionality

Dose-proportionality of TAS3351 and TAS-05-14317 PK parameters on Day -3 and Day 15 will be evaluated based on both power regression analysis and one-way analysis of variance (ANOVA). Dose-proportionality will be assessed in C_{max} , AUC_{last} , AUC_n , AUC_{inf} on Day -3, and C_{max} , AUC_{last} , AUC_n on Day 15.

Regression analysis using power model

The power regression analysis will be performed using the following model:

$$\log(\text{AUCs or } C_{\text{max}}) = \alpha + \beta \times \log(\text{dose})$$

This model will be used to investigate the null hypothesis ($H_0: \beta=1$) with calculating 90% confidence intervals (CIs) for the power constant (β) with insignificance ($p < 0.05$) of testing the lack of fit. For a given parameter, a minimum of 3 values per dose level must be available for that dose level to be included in the power model.

One-way ANOVA

Prior to the analysis, dose-dependent parameters (C_{max} and AUCs) will be normalized with dose. All dose-normalized PK parameters will be log-transformed prior to the analysis, and then the differences in the means of dose levels will be tested by one-way ANOVA.

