3.3. Determination of Sample Size

Part A:

Part A1: Phase 1 Dose Escalation

There will be up to 40 evaluable patients enrolled using the BOIN (Bayesian optimal interval design) design, [REDACTED] A minimum of 3 patients at each dose level are required.

Part A2: Backfill patients

Approximately 20 patients will be added for “back-fill” cohorts as needed in the Phase 1 Dose Escalation. The additional information from these “back-fill” patients will broaden the amount of safety and preliminary anti-tumor activity data for TAS3351 at a potential active dose levels to inform the selection of the RP2D of TAS3351.

Part B: Phase 1 Dose Expansion

Approximately 40 patients (20 patients per cohort) will be enrolled in the Dose Expansion part of this study. Sample size considerations were based on estimating the proportion of responders with certain precision. If there will be 9 responders, a sample size of 20 patients per cohort would allow to exclude the current standard of care ORR of 25% (90% CI: 27.4%, 68.0%) at 2-sided significance level of 10%.

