5.7.2. Plasma PK Parameters

5.7.2.1. PK Parameter Calculation

For the Dose Escalation part (Part A1) of the study, PK parameters will be calculated by standard noncompartmental analysis (NCA) on Day -3 of PK Lead-in (for QD dosing) or Day 1 (for BID dosing, if applicable) and Day 15 (for both QD and BID dosing, if applicable) of Cycle 1.

The calculation of PK parameters in plasma will be based on the actual time after the dosing. The time of collection of the pre-dose sample will be set to zero for calculating PK parameters. The plasma concentration data for the calculation of PK parameters will be handled as described in Section 5.7.1.1 except that plasma concentrations below the LLOQ appearing in terminal time-points will be treated as missing.

Plasma PK parameters will be estimated as follows:

- C_{\max} (Maximum observed concentration);
- T_{\max} (Time of maximum observed concentration);

C_{\max} and T_{\max} are obtained from experimental observations. If C_{\max} occurs at 2 or more time points, T_{\max} is assigned to the time of the earliest occurrence. In determining T_{\max} , the actual time of the plasma sample relative to the dosing time will be used.

- AUC_{last} (Area under the curve from the time of dosing to the time of last quantifiable concentration);
- AUC_n (Area under the curve from the time of dosing to time n);

AUCs will be calculated using the linear log trapezoidal rule. AUC_n will be calculated by the program as a partial area depending on the dosing interval. Prior to calculating AUCs and $T_{1/2}$ (terminal elimination half-lives), the individual plasma concentrations by time profiles are evaluated on an individual basis as to their suitability for inclusion in these calculations. In calculating AUCs, plasma concentrations that are listed as BQL are treated as missing, except for the following cases: for single-dose profiles, BQL concentrations prior to the first quantifiable concentration will be set to 0; for multiple-dose profiles, BQL concentrations at the beginning of the profile may be set to 0 or C_{\min} . The pre-dose sampling time will be set to 0. For single-dose profiles, the concentration at pre-dose will be set to 0.

- $T_{1/2}$ (Terminal half-life)

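### The SAP prints the dose-proportionality lack-of-fit condition the wrong way round, and does not say how the slope interval or a non-significant test is to be read

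*SAP*

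**What the plan says.** SAP 5.7.2.4 gives two methods for C_max and the AUCs on Day -3 and Day 15.

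- **Power model.** Log exposure is regressed on log dose with slope β. "This model will be used to investigate the null hypothesis" β = 1, "with calculating 90% confidence intervals (CIs) for the power constant". The same sentence adds a condition on the result "of testing the lack of fit": it names insignificance as the requirement, but the bracket after that word reads p < 0.05. A dose level enters only if it has enough data: "a minimum of 3 values per dose level must be available for that dose level to be included in the power model".
- **ANOVA.** Exposures are divided by dose and log-transformed, and then "the differences in the means of dose levels will be tested by one-way ANOVA".

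The section gives no limits for reading the CI, no significance level for the slope test or the ANOVA, no sentence on when proportionality is concluded, and no instruction for the case where the power model does not fit. Protocol 8.3.2 says only that a statistical method will be used in Part A1.

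On numbers, SAP 3.3 says "There will be up to 40 evaluable patients enrolled using the BOIN" design and "A minimum of 3 patients at each dose level are required". Protocol 6.1.1 sets a maximum of 15 per level and plans six levels from 50 to 700 mg/day.

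**The concern.** There are two separate problems.

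1. **The lack-of-fit condition contradicts itself.** At the 5% level, insignificance means p ≥ 0.05. If the printed inequality is programmed, a well-fitting power model is set aside and a badly fitting one is kept.
2. **Both tests have proportionality as their null.** Failing to reject β = 1, or failing to find a difference between dose-normalised means, may reflect proportional exposure or may reflect few patients and wide variability. With no limits for the CI and no statement on how non-significance is to be read, the report's author has no rule for telling these apart.

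What is at stake is the wording of the dose-proportionality conclusion in the study report.

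**Working it through.** The documents give no power or precision figure for dose-proportionality, so there is nothing of the plan's own to reproduce.

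**Step 1: the printed condition.** If the power model is exactly true, a 5% lack-of-fit test gives p < 0.05 in about 5% of trials by construction. A simulation of 20,000 trials gave 5.0% with 3 per level and 5.2% with 6 per level. The literal condition therefore admits a correct model about 5% of the time. The corrected condition admits it about 95% of the time.

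**Step 2: inputs for the slope test.**

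- Doses 50, 100, 200, 350, 500 and 700 mg (Protocol Table 5), a 14-fold range.
- Natural logs 3.912, 4.605, 5.298, 5.858, 6.215 and 6.551, with mean 5.407. The sum of squared deviations is 5.054 for one patient per level, so Sxx = 5.054n for n per level.
- Assumed, not in the documents: equal n per level, with n = 3, 4 or 6; between-patient CV of 30%, 50% or 60%; true slope 0.8.
- The values of n are illustrative. The documents give a minimum of 3, a maximum of 15 and up to 40 in total, or 40/6 = 6.7 per level if spread evenly.

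**Step 3: what slope 0.8 means.** Dose-normalised exposure at 700 mg relative to 50 mg is 14^(0.8 - 1) = 14^(-0.2) = 0.59, a 41% shortfall.

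**Step 4: formulas.**

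- σ = √ln(1 + CV²)
- SE(β) = σ/√Sxx
- 90% CI half-width = t(0.95, 6n - 2) × SE
- The chance that the CI contains 1 comes from the noncentral t distribution with noncentrality (0.8 - 1)/SE.

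Worked case, CV 60% and n = 3:

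- σ = √ln(1.36) = 0.5545
- SE = 0.5545/√(3 × 5.054) = 0.142
- t(16 df) = 1.746, so the half-width is 0.25
- Noncentrality = -0.2/0.142 = -1.40
- The CI contains 1 in 62% of trials.

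**Step 5: results, true slope 0.8.**

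| Assumed CV | 3 per dose | 4 per dose | 6 per dose |
|---|---|---|---|
| 30% | 19% | 9% | 2% |
| 50% | 53% | 42% | 26% |
| 60% | 62% | 53% | 38% |

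Entries are the chance that the 90% CI for β still contains 1.

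**Step 6: the ANOVA.** It spreads the same departure over 5 degrees of freedom. At an assumed 5% level and CV 60%, it is non-significant in 88%, 84% and 76% of trials with 3, 4 and 6 per dose.

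**Step 7: fewer levels.** If escalation stopped after four levels (50-350 mg) with 3 per level, power to reject β = 1 at slope 0.8 would be 49% at CV 30% and 15% at CV 100%. The CI would then contain 1 in 51% to 85% of trials.

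**The case against.** The strongest reply has four parts.

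- **The inequality is a slip.** The word insignificance shows the intent, and p < 0.05 probably records the test level. That is likely. But this is the text from which the analysis is programmed, and neither the SAP nor Protocol 8.3.2 settles it. The correction stands.
- **The plan never says that non-rejection means proportional.** A reader might infer that the section rests on failing to reject β = 1. The documents do not support that: the SAP says the hypothesis is investigated and that a CI is calculated, so imprecision would be visible. What remains is the absence of any statement on how the CI or a non-significant result is to be read.
- **Small cohorts do not rule out a useful answer.** A reader might infer that a few patients per dose can never show proportionality. That is too strong. The slope pools all levels over a 14-fold range, and at CV 30% with 6 per dose a slope of 0.8 is missed in only 2% of trials. The size of the problem depends on a CV that the documents do not give.
- **Nothing turns on it clinically.** A reader might infer that a wrong call would misdirect escalation, BID dosing or backfill doses, because Protocol 6.1.1 mentions saturation of exposure and 4.2.1 mentions PK simulation. No passage ties those decisions to this test. Escalation follows the BOIN DLT rules, BID dosing follows a review of PK, pharmacodynamic and/or safety data, and backfill doses follow safety, tumor shrinkage or exposure thresholds. SAP Section 1 describes output for the study report. This part of the reply holds in full.

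**Conclusion.** The reversed lack-of-fit condition is a definite error and needs no assumption to establish. The second problem is real but conditional: a non-significant slope test or ANOVA is weak evidence of proportionality at moderate to high variability or with few levels, and considerably better evidence at low variability. The range of 2% to 62% in the table rests on assumed CVs of 30% to 60%, equal numbers per dose, six levels and a true slope of 0.8. This is a minor point, confined to the PK conclusion in the study report.

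**What to change.** In SAP 5.7.2.4:

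1. State the lack-of-fit condition as not significant (p ≥ 0.05). If p < 0.05, report dose-normalised exposure by dose level rather than rely on a single slope.
2. Report the slope with its 90% CI as an estimate. Say that neither a non-significant slope test nor a non-significant ANOVA will be taken as evidence of proportionality, and use the ANOVA descriptively.
3. If a conclusion on proportionality is wanted, state in advance the interval for β within which the whole 90% CI must lie, and allow the result to be inconclusive.

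The interval in item 3 is the sponsor's choice and needs care. Limits of 1 ± ln(2)/ln(14), or 0.74 to 1.26, contain the slope of 0.8 used above. They would declare it proportional in about 31% of trials at CV 30% with 6 per dose. Limits of 1 ± ln(1.25)/ln(14), or 0.92 to 1.08, would pass a truly proportional drug only about 0% to 3% of the time with 3 to 6 per dose at CVs of 30% to 100%.

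The cost is a few SAP sentences, with no change to data collection or to patients. The downside is that the conclusion may often be inconclusive.

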5.8. Pharmacodynamic and Other Biomarker Analyses

All biomarkers except for C797S EGFRmt in this study are for exploratory purpose. Biomarker data will be investigated on this basis and will not be listed in this SAP.

5.9. Other Analyses

The serum chemistry KL-6, the vital sign SpO_2 , and the viral tests for HBV and HCV will be assessed for patients who are accrued only at sites in Japan. The analyses for these Japan specific assessments are as follows.

KL-6

Descriptive statistics will be presented for KL-6 using SI Units at each scheduled visit. Change from baseline will be summarized in a similar manner. All KL-6 data will be presented in by-patient listings.

SpO_2

SpO₂ will be summarized with descriptive statistics by scheduled time point. Change from baseline will be summarized in a similar manner. All SpO₂ data will be presented in by-patient listings.

Viral Tests

Viral tests include HBc antibody, HBs antibody, HBV DNA, and HCV RNA. The data for all of these viral tests will be presented in by-patient listings.

6. CHANGES IN PLANNED ANALYSIS

All analyses specified in this SAP are consistent with the study protocol (Protocol 10073010 Amendment 2 (07-July-2023)).

SAP Version	Major Updates	Rationale
1.0	Original	
2.0	
 Section 4.1: The definition of the study period was added for clarity for the analysis Section 5.5.1: Unconfirmed response was added Section 5.5.4: The Intracranial ORR analysis for Part A as assessed by investigator was added for clarity Section 5.5.5: The Intracranial DoR statistical method for Part A as assessed by investigator was added for clarity Section 5.6.1.1: Actual Dose intensity per cycle and relative dose intensity per cycle summaries were removed. Cumulative dose calculation was changed to the sum of the doses administered to a patient during the treatment period by removing the division by BSA. Such changes were fit for purposes. Section 5.6.1.2: The number and percentage of patients with at least one dose increase and reason for the dose increase were removed. The number of dose increases (1, 2, >2) was removed. Section 5.6.2.1: Summaries of death were corrected from deaths within (30(+3) days and deaths after 33 days to deaths within 30 days and deaths after 30 days, respectively. This approach is consistent with general practice. Section 5.6.2.2-5: The analysis was changed to by dosing cohorts by grade. Section 5.6.4: Amylase and lipase were added with amendment 2. . Section 5.6.6: Additional details of ECG data collection were added for ease of understanding analysis. Section 5.6.7: Additional details of time-matched QTcF versus plasma concentration analysis methodology were added for ease of understanding analysis. Section 5.7.2.4: The analysis of dose proportionality further specified that for a given parameter, a minimum of 3 values per dose level must be available for that dose level to be included in the power model. 	Added/updated based on protocol amendment 1 & 2, and provided further details to clarify the analysis and removed content that was not applicable

7. DEFINITIONS AND CONVENTIONS FOR DATA HANDLING

7.1. Baseline Period

Baseline evaluations or events will be defined as evaluations or events that occur before the date and time of the first dose of study drug. Evaluations on the same date and time of the first dose of study drug will be considered as baseline evaluations.

In cases where the time (onset time of event or evaluation time and dosing time) is missing or not collected, the following definitions will apply:

- Pre-treatment AEs will be defined as AEs with an onset date prior to but not including the day of the first dose of study drug
- Baseline evaluations will be defined as evaluations with a date on or prior to the day of first dose of study drug

If there are multiple valid assessments, the assessment that is closest to the day (and time if collected) of the first dose of study drug will be used as the baseline in the analyses. If multiple assessments are collected on the same date (and time, if collected), the assessment with the latest database entry date (and time, if collected) will be considered as baseline.

7.2. Post-Baseline Period

On-treatment AEs will be defined as AEs with an onset date and time on or after the date of the first dose of study drug (or with an onset date on or after the day of first dose of study drug if time is not collected or is missing). For patients who are off study drug, AEs will be included if event occurred within a safety window of 30 days after the last dose of study drug. No “subtracting rule” will be applied when an AE occurs both pre-treatment and post-treatment with the same preferred term and grade.

On-treatment evaluations will be defined as evaluations taken after the day (and time, if collected and not missing) of first dose of study drug. For patients who are off study drug, evaluations should be within a safety window of 30 days after the last dose of study drug.

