1.3. SCHEDULE OF EVENTS

Table 1: Schedule of Events for Phase 1 (Parts A and B)

Procedure	Screening Period Within 28 Days prior to first dose	Treatment Period							Follow-up Period		Notes
		PK Lead-in ^a	Cycle 1 (21 days)			Cycle 2 (21 days)		Cycles ≥ 3 (21 days)	Safety Follow-up ^b	Survival Follow-up	
		Day -3	Day 1	Day 8 (± 1 day)	Day 15 (± 3 days)	Day 1 (± 3 days)	Day 8 (± 3 days)	Day 1 (± 3 days)	30 (+3) days after last dose		
EGFR C797S status (pre-screening informed consent)	See Notes										Only if central pre-screening done. Can be done any time prior to screening.
Written informed consent (main study)	X										To be obtained prior to any study related procedures.
Review inclusion / exclusion criteria	X										All patients in Part A2 and B must have documented C797S EGFRmt. See Section 4.1 and Section 4.2
Demographics/ Medical history	X										Including prior antitumor treatment
Physical examination	X	X	X	X		X		X	X		Within 24 hours prior to dosing. May be symptom directed during treatment period. Examination of skin should be performed at each timepoint. See Section 7.1
Ophthalmological examination	X	As clinically indicated							X		See Section 7.1.5
Height and weight	X	X	X			X		X	X		Height at screening only
Vital signs	X	X	X	X	X	X	X	X	X		Heart rate, blood pressure, and body temperature. See Section 7.1
Hematology	X	X	X	X	X	X	X	X	X		Assessment prior to first day of dosing may be done up to 72 hours prior to dosing

											(Section 7.1.4) All other assessments may be done within 24 hours prior to dosing See Section 7.1
Chemistry	X	X	X	X	X	X	X	X	X		Assessment prior to first day of dosing may be done up to 72 hours prior to dosing (Section 7.1.4) All other assessments may be done within 24 hours prior to dosing See Section 7.1
Coagulation	X	X	X			X		X	X		Assessment prior to first day of dosing may be done up to 72 hours prior to dosing (Section 7.1.4) All other assessments may be done within 24 hours prior to dosing See Section 7.1
Urinalysis	X	X	X			X		X	X		Assessment prior to first day of dosing may be done up to 72 hours prior to dosing (Section 7.1.4) All other assessments may be done within 24 hours prior to dosing. See Section 7.1
Pregnancy test	X	X	(X)			X		X			For WOCBP only: Serum pregnancy test required at screening only. See Section 7.1 (X) not required for patients in Part A1

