^b The 30-day Safety Follow-up visit should be performed 30 days (± 3 days) following the last dose of study therapy. If the patient starts new anticancer therapy within 30 days of the last dose of study medication, the 30-day Safety Follow-up visit should be performed before the start of new anticancer therapy. Only if the patient is unable to return to the study site, a follow-up phone call can be made by the study site to collect any new safety information that occurred during the Safety Follow-up period.

^c ECG assessment for C1D1, and D1 of C2 and beyond should be conducted pre-dose (up to 30 minutes prior to dosing). ECG should be performed on D1 of every cycle. All ECGs should be performed in triplicate on Day 1 of Cycles 1 to 3 for all patients. After C3D1, ECGs are not required to be performed in triplicate unless clinically indicated.

Abbreviations: AE=adverse event; C=cycle; cfDNA=cell-free DNA; D=day; DLT=dose-limiting toxicity; ECG=electrocardiogram; ECOG=Eastern Cooperative Oncology Group; EOT=end of therapy; ICF=informed consent form; MUGA=multi-gated acquisition scan; PD=progressive disease; PK=pharmacokinetics; QD=once daily; RECIST=Response Evaluation Criteria in Solid Tumors; SAE=serious adverse event; WOCBP=women of childbearing potential

Note: (X) = See notes for details.

Table 2: Schedule of Events for Phase 2 (Part C)

Procedure	Screening Period Within 28 Days prior to first dose	Treatment Period			Follow-up Period		Notes
		Cycle 1 (21 days)		Cycle ≥2 (21 days)	Safety Follow-up ^a	Survival Follow-up	
		Day 1	Day 8 (±1 day)	Day 1 (±3 days)	30 (+3) days after last dose		
EGFR C797S status (pre-screening informed consent)	See Notes						Only if central pre-screening done. Can take place any time prior to screening
Written informed consent (Main study)	X						To be obtained prior to any study related procedures. Can take place any time before Day 1
Review inclusion / exclusion criteria	X						All patients must have documented C797S EGFR mt
Demographics/Medical history	X						Including prior antitumor treatment
Physical examination	X	X		X	X		Within 24 hours prior to dosing. May be symptom directed during treatment period. Examination of skin should be performed at each timepoint.
Ophthalmological examination	X	As clinically indicated			X		See Section 7.1.5
Height and weight	X	X		X	X		Height at screening only
Vital signs	X	X	X	X	X		Heart rate, blood pressure, body temperature

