2.2.1.7. Eye Disorders

In nonclinical studies, atrophy of corneal epithelium was observed.

Potential side effects and risks anticipated are keratitis, corneal erosion, corneal ulcer, vision blurred, corneal opacity, and eye pain. Monitoring of patients for eye disorders will be conducted by ophthalmological examinations at baseline and any time during study treatment if clinically indicated. Patients should be advised to contact their study physician if experiencing any change in vision.

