4. STUDY PERIODS, TREATMENT REGIMENS, AND POPULATIONS FOR ANALYSIS

4.1. Study Periods for Analyses

Study periods are defined in [Table 2](#).

Table 2: Definition of Study Periods for Analysis

Period	Definition
Study Period	From the day of the first ICF signature to the last day of Survival Follow-up Period
Screening Period	From the day of informed consent form (ICF) signature (up to 28 days before first dose) to the day before the first dose
Treatment Period	From the date of first dose of study drug (Day 1/PK lead-in for part A1) to the last day of dosing.
Safety Follow-up Period	30 (+3) days after the last day of dosing
Survival Follow-up Period	From the last day of Safety Follow-up period to death, or study completion, whichever happens first

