5.6.12. Ophthalmological Examination

The result of ophthalmological examination will be summarized with the number and percentage of each category by scheduled time point, examination, and tested eye (left, right). Also, it will be presented in by-patient listing.

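### SAP 7.2 closes the evaluation window at day 30 although on-time Safety Follow-up visits run to day 33, and SAP 5.6.12 gives on-treatment eye examinations no row in the summary table

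*SAP*

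**What the plan says.** **Evaluation window.** SAP 7.2, headed Post-Baseline Period, defines on-treatment evaluations and then bounds them once treatment has stopped: "For patients who are off study drug, evaluations should be within a safety window of 30 days after the last dose of study drug". It gives no allowance beyond day 30 and makes no exception for the Safety Follow-up visit.

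**Visit window.** SAP Table 2 (section 4.1) defines the Safety Follow-up Period as "30 (+3) days after the last day of dosing", and protocol Table 4 agrees. For Parts A and B, the only parts this SAP covers, the column heading of protocol Table 1 reads "30 (+3) days after last dose". Footnote b to the same table differs: "The 30-day Safety Follow-up visit should be performed 30 days (± 3 days) following the last dose of study therapy". It adds that if new treatment starts within 30 days of the last dose, "the 30-day Safety Follow-up visit should be performed before the start of new anticancer therapy".

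**Eye examination.** Protocol Table 1 marks it at Screening and at Safety Follow-up, with "As clinically indicated" across the treatment period. Protocol 2.2.1.7 describes the same monitoring: "ophthalmological examinations at baseline and any time during study treatment if clinically indicated". SAP 5.6.12 summarizes the results by "number and percentage of each category by scheduled time point, examination, and tested eye (left, right"), and adds a by-patient listing.

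**The concern.** A patient who attends on day 31, 32 or 33 has complied with the protocol, yet the SAP's evaluation window has already closed. Whether the last off-drug laboratory value, ECOG score or local ECG counts would then depend on which permitted day the patient came. Two programmers could also produce different tables from the same data, because the SAP does not say which summaries apply the 7.2 limit.

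The eye-examination gap does not depend on attendance day. Corneal epithelial atrophy was seen in nonclinical studies, and corneal ulceration has its own row in the protocol's dose-modification table (Table 10). SAP Table 1 lists ophthalmologic assessment under the primary objective of dose escalation and again under safety in Part B. A table limited to scheduled time points would show Screening and roughly one month off drug. It would not show the examinations done on treatment, which are the ones prompted by a clinical indication.

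**Working it through.** The plan states no figure for this, so there is none to reproduce. The check is a day count, followed by a comparison of the SAP's own summary rules.

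**1. Permitted visit days outside the window.** Inputs: evaluations accepted through day 30 inclusive (SAP 7.2); visit days 30 to 33 (SAP Table 2, protocol Table 4, heading of protocol Table 1) or 27 to 33 (footnote b).

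- Under +3: days 30, 31, 32, 33. Outside: 31, 32, 33, which is 3/4 = 75% of permitted days.
- Under ±3: days 27 to 33. Outside: 31, 32, 33, which is 3/7 = 43% of permitted days.

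Both texts end on day 33, so the mismatch exists whichever one is kept.

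**2. From days to visits.** The documents give no distribution of visit days, so this step rests on assumptions. Let f be the fraction of permitted days outside (3/4 or 3/7). Let e be the share of patients seen early because new therapy is starting; those visits fall inside the window. With the remaining visits spread evenly, the share outside is (1 − e) × f.

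| e | +3 reading | ±3 reading |
|---|---|---|
| 0 | 75% | 43% |
| 20% | 60% | 34% |
| 33% | 50% | 29% |
| 50% | 37.5% | 21% |

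If instead visits cluster on day 30, with share q on that day under +3 and e = 0, the share outside is 1 − q: 60% at q = 40%, 50% at q = 50%, 20% at q = 80%.

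**3. Which summaries are exposed.**

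- Worst post-baseline ECOG grade (SAP 5.6.9) and the investigator ECG-interpretation shift to the worst post-baseline result (SAP 5.6.6) both depend on what counts as post-baseline. Protocol Table 1 schedules ECOG and a local ECG at Safety Follow-up.
- Worst laboratory grade (SAP 5.6.4) uses all post-baseline assessments, unscheduled visits included. That wording does not itself set an end date, and 7.2 is the only section that defines the post-baseline period.
- The QTcF category summary names the on-treatment period but uses central ECGs. Safety Follow-up has only a local ECG, so this summary loses nothing from that visit.

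**4. Eye examinations.**

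| Assessment | Rule for unscheduled or worst values in the SAP |
|---|---|
| Laboratory | Worst grade, unscheduled visits included (5.6.4) |
| ECG interpretation | Shift to worst post-baseline (5.6.6) |
| ECOG | Shift to worst post-baseline (5.6.9) |
| Eye | None; scheduled time points only (5.6.12) |

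Protocol Table 1 gives the eye examination one scheduled post-baseline time point, at Safety Follow-up. An examination done on treatment because it was indicated has no scheduled time point, and so no row.

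**5. After the change.** With the window extended to day 33, 0 of 4 permitted days (+3) and 0 of 7 (±3) fall outside.

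**The case against.** The best case on the other side has four parts.

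*The 7.2 sentence may not govern these tables.* It qualifies on-treatment evaluations, and SAP 5.6.12 and the by-visit laboratory, vital-sign and ECOG summaries do not repeat it. Safety Follow-up is a scheduled column, so a by-time-point table could include it whatever the day. This stands in part: the SAP never says that 5.6.12 applies the limit. It does not help the worst post-baseline summaries, which have no other definition to use.

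*Visit mapping may be settled elsewhere.* SAP 7.4 sends other data-handling rules to a separate document that is not available here. That document might resolve the point, but the SAP text as it stands does not.

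*Thirty days was a deliberate convention.* The SAP's change table moved the death summaries from 30 (+3) to 30 days as general practice. That concerns deaths. It gives no reason for applying the same limit to evaluations tied to a visit that may be made on day 33.

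*Eye toxicity is captured in other ways.* This stands. Protocol 7.1.5 requires clinically significant eye findings to be reported as adverse events, SAP 5.6.2.2 tabulates treatment-emergent events, and 5.6.12 provides a listing. A reader might infer that on-treatment corneal toxicity would go unreported, and the documents do not support that. What is missing is the examination summary itself.

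**Conclusion.** The plan has two separate gaps, both modest. First, the evaluation window ends three days before the last permitted Safety Follow-up day. On-time evaluations on days 31 to 33 are therefore outside it for summaries that rely on 7.2. This assumes that post-baseline in 5.6.4, 5.6.6 and 5.6.9 takes its meaning from 7.2. Second, clinically indicated on-treatment eye examinations do not enter the 5.6.12 table, whatever day the patient attends Safety Follow-up.

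A reader might infer that most on-time visits, and with them most Safety Follow-up eye examinations, are lost. The documents do not show this. It needs the +3 text, few visits brought forward and little clustering on day 30. Under ±3 with an even spread it is never a majority, and 5.6.12 does not state that it applies the cut at all. The share of visits affected is unknown.

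Nor does the point reach the QTcF categories, DLT incidence or ORR. The wider visit window in the extension phase adds nothing material, since that phase follows completion of the scientific evaluation and schedules no eye examination.

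**What to change.** 1. **SAP 7.2:** accept evaluations up to 30 days after the last dose, or at the Safety Follow-up visit if made by day 33 and before new anticancer therapy. State which summaries use this window. Leave the adverse-event and death windows at 30 days; the adverse-event window matches the collection period in protocol 10.1.3.
2. **SAP 5.6.12:** add a shift for each eye from baseline to worst post-baseline finding, including unscheduled examinations.
3. **Protocol Table 1:** reconcile the column heading (+3) with footnote b (±3).

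The cost is a short wording change, one added table and one protocol correction, all on data already collected. The downside is that a few off-drug values from days 31 to 33 will count as on-treatment.
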